Acute physiological response to aerobic exercise	
 • Heart rate • Blood pressure • Oxygen saturation 
 • Cerebral blood flow (CBF) velocity 
 • Oxygen consumption ($\dot{V}O_2$) 	
Only one study has investigated the use of aerobic exercise in the acute phase of stroke (44). The only physiological variable reported was mean exercise heart rate. Collecting more in-depth physiological data will improve the mechanistic knowledge of how aerobic exercise influences cerebral perfusion and recovery from injury. Furthermore, monitoring heart rate, blood pressure and oxygen saturation in real-time will improve the safety of exercise prescription.
 
Heart rate will be measured telemetrically via a chest strap or using wireless ECG; brachial blood pressure will be measured with an oscillatory monitor; and peripheral oxygen saturation will be measured with a fingertip pulse oximeter.
 
CBF velocity is a non-invasive proxy measure of cerebral perfusion (111). Moderate-intensity aerobic exercise increases CBF velocity by 10-30% (30). Increasing blood flow to the peri-infarct area may enhance reparative processes and promote neuroplasticity (24–26,30,31,36,37,95,112). We will use a transcranial Doppler (TCD) ultrasound device to determine changes in CBF velocity measured bilaterally at the middle cerebral arteries. A specially designed, comfortable headset will be used to fix the ultrasound probes in place during exercise sessions.
 
To minimise time burden, CBF velocity will be measured a maximum of two times per participant. Both the control group and the intervention group will have resting CBF velocity measured on the second study day (t_1) and the sixth study day (t_5). For the intervention group only, we will record changes in CBF velocity throughout the exercise sessions immediately after resting measures. Measuring resting CBF velocity will enable us to understand how this variable changes in the first week of stroke under conditions of usual care and aerobic exercise training. Furthermore, as the aerobic exercise duration progresses throughout the 5-day intervention from 10 to 30 minutes, a repeated measure (first vs. fifth exercise session) will help to identify if there is a dose-response relationship between exercise duration and change in CBF velocity (intervention group only). Hypoallergenic ultrasound gel and nitrile gloves will be used. If a patient has a known allergy to ultrasound gel, this test will be excluded.
 
During moderate-intensity aerobic exercise, increased energy turnover within working muscle leads to increased $\dot{V}O_2$ and CO_2 production (30). CO_2 is a potent vasodilator and is a key regulator of CBF (30). $\dot{V}O_2$ can be used to estimate the energy expenditure of physical exercise. Combined measurement of $\dot{V}O_2$ and end-tidal CO_2 enables the estimation of the metabolic

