---	---	--

	
 • End-tidal carbon dioxide (CO₂) • Mature brain-derived neurotrophic factor (mBDNF) • Platelet count • Plasma volume 	
stress and thereby intensity of exercise (61). Both $\dot{V}O_2$ and end-tidal CO₂ can be measured concurrently using an expired gas analysis system. Expired gas will be collected via a non-invasive face mask. $\dot{V}O_2$ and end-tidal CO₂ will be measured in the intervention group only during the fifth exercise session.
 
mBDNF is a key mediator of neuroprotection, neuroplasticity, memory formation and learning (28). Aerobic exercise transiently increases the systemic production and secretion of mBDNF (29). Platelets are a primary storage site of mBDNF in the blood (29). Aerobic exercise stimulates the release of platelets from the spleen which increases the circulating level of mBDNF (29,37). To accurately determine exercise-induced changes in serum mBDNF independent of platelet count, mBDNF concentration will be calculated per platelet. In addition, blood plasma contains a freely circulating pool of mBDNF that is not bound to platelets. Possible sources of plasma BDNF include the brain, skeletal muscle, peripheral blood mononuclear cells and vascular endothelial cells (29). Measurement of plasma mBDNF is necessary to determine if cellular sources of BDNF are secreted into circulation during exercise. However, during moderate-intensity exercise, water shifts from plasma into both the interstitial and intracellular fluid compartments of contracting skeletal muscle. Thus it is important to correct for changes in plasma volume to prevent erroneous interpretations of changes in mBDNF concentration (113). In sum, by assessing changes in the total mBDNF system (serum, volume-corrected plasma, platelets, and mBDNF per platelet), it is possible to quantify cellular sources of denovo mBDNF, and to differentiate this from changes in mBDNF that result from altered blood plasma volume and movement of mBDNF between plasma and platelet pools (29).
 
Due to the invasive nature of venous blood sampling and the expense of analysing mBDNF, we have chosen to limit blood sample collection to a maximum of two timepoints per participant at t_5: 1) baseline (both groups), and 2) post-exercise (intervention group only). We have chosen to measure mBDNF at the fifth aerobic exercise session which is 30 minutes in duration. This exercise duration has consistently been shown to increase circulating mBDNF (29). Hypoallergenic nitrile gloves, dressings and plasters will be used.

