12.3.3. Aerobic exercise

The exercise protocol will begin with a 5-minute passive cycling period (20 revolutions per minute [rpm]), where the participant will be relaxed (no exertion) and the bike will rotate the participant's legs to mobilise the lower limb joints and increase venous return. Subsequently, the participant will complete a low- to moderate-intensity warm-up phase. Starting in the lowest gear, the participant will be instructed to cycle a self-selected cadence aiming for an intensity equivalent to 'light' (11/20) on the RPE scale (90). At 60s and at each subsequent minute, the operator will increase the cycle gear by one level until a target RPE of 13 ('somewhat hard') is achieved. The warm-up duration will be individualised for each participant based on time taken to reach RPE 13. When RPE 13 is reached, the conditioning phase will commence and the participant will be instructed to maintain a consistent cadence ($\pm 10\%$) for 5-min. After which, passive mode (20 rpm) will be activated and the participant will be asked to rest for 1-min. The number of 5-min conditioning bouts will increase by one bout per session. The first session will contain 2 bouts (total = 10 mins), and the fifth session will contain 6 bouts (total = 30 mins). The rationale for this progressive design was developed with input from researchers, healthcare practitioners and people affected by stroke (see PPI section, 13.2.). Briefly, it was considered that starting with 30-min of aerobic exercise in session 1 may be too difficult for some patients due to fatigue, whereas a gradual progression in exercise duration would be more tolerable. Throughout the warm-up and conditioning phases, RPE will be measured in the last 15s of each minute, and the cycle gear will be adjusted accordingly if RPE deviates away from target. The target exercise intensity (moderate) will remain constant during the work intervals of the conditioning phase. To ensure that the intervention is tolerable (i.e. the conditioning phase can be completed), the cycling gear (resistance) will be adjusted according to the participant's level of function and RPE at that particular time. All performance metrics displayed on the MOTOMed interface (Watts, gear, left-to-right symmetry and distance) will be concealed from the participant with the exception of cadence (rpm). After the conditioning phase, the participant will undertake a graduated cool-down for 5 minutes and then will be instructed to relax whilst a final 2-min passive cycling recovery phase is completed.

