
The day after completing the first exercise bout, participants will undertake a single aerobic exercise session per day for 4 days (5 exercise sessions in total). If patients are discharged earlier, study participation will terminate on the day of discharge. The workload that elicited an RPE of 13 at the start of the conditioning phase in the first aerobic exercise session will be used to guide the initial workload for the conditioning phase in subsequent sessions.

Number of repetitions (rpm multiplied by minutes) completed during the warm-up,

conditioning phase and cool-down will be included within therapy dose calculations. Verbal communication provided by the operator will be standardised (detailed in Table 6, Appendix).

Through consultations with stroke survivors and healthcare practitioners we acknowledge the need for a flexible exercise protocol. It was expressed to us that patients' level of fatigue and physical function may fluctuate throughout the duration of hospital stay depending on various intrinsic and extrinsic factors. Thus, the workload used for each exercise session will be a collaborative choice made between the researcher and the participant.

[figure not shown]

Figure 5. Schematic diagram of 5-day exercise protocol.

Note: Blue = passive cycling (no exertion) = 5 minutes; brown = warm up/cool down; pink = active cycling (moderate intensity). Active cycling duration = 5 minutes per bout. Passive recovery intervals = 1 minute (blue).

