14.2.1. Protocol amendments based on patient and public involvement

We initially proposed a fixed 30-minute bout of aerobic exercise per session. However, the PPI consensus was that this duration may be too long for some individuals due to severe fatigue and disability after stroke. We responded to this issue with two solutions: 1) by adopting an interval training design consisting of shorter moderate-intensity aerobic exercise bouts interspersed with rest intervals; and 2) by gradually increasing the total exercise duration per session over 5 days. It was also noted that NHS staff capacity is reduced at weekends, therefore the intervention should be delivered over 5 working days. A key point raised at the PPI events was that aphasia may be a barrier to participation due to issues with reading and speech comprehension. We will therefore use aphasia-friendly design and communication techniques wherever possible to increase the accessibility of our study information and intervention protocol. In addition, discussions from the PPI events inspired the idea of assessing exercise self-efficacy and optimism. A summary of the PPI events is attached to the IRAS form.

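### The comparison of session 1 with session 5 cannot attribute a change in the cerebral blood flow response to exercise duration, because day since stroke, prior training and the face mask change with it

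*Protocol*

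**What the plan says.** Table 4 in Section 9.2 limits the burden of the measurement: "CBF velocity will be measured a maximum of two times per participant". Both arms have resting CBF velocity measured at t1 and t5. In the intervention arm only, "we will record changes in CBF velocity throughout the exercise sessions immediately after resting measures". Exercise lengthens from 10 to 30 minutes over the five days, so the table states that a repeated measure, first against fifth session, "will help to identify if there is a dose-response relationship between exercise duration and change in CBF velocity".

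Other parts of the protocol fix what differs between those two sessions:

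- **Duration.** Section 12.3.3 prescribes two 5-minute bouts in the first session and six in the fifth.
- **Prior sessions and elapsed time.** Section 12.3.3: "The day after completing the first exercise bout, participants will undertake a single aerobic exercise session per day for 4 days". Section 14.2.1 adds that "the intervention should be delivered over 5 working days", so a weekend can lengthen the gap.
- **Gas analysis.** Oxygen consumption and end-tidal CO₂, collected through a face mask, "will be measured in the intervention group only during the fifth exercise session". Table 3 shows one tick for end-tidal CO₂ and two for the exercise change in CBF velocity.

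The protocol states no time-matched comparison, adjustment or limitation for the duration inference.

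**The concern.** A dose-response claim needs the dose to vary while other influences on the response stay fixed or can be separated. Here the dose is tied to the calendar. Every intervention participant is prescribed the short session first and the long one last, and no one exercises in the control arm.

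The protocol itself gives reasons to expect the other factors to matter. Table 4 says biologically distinct events occur within the first week and plans to study how resting CBF velocity changes over that week. Section 3 says infarct expansion may continue until about day 4. Section 9.5 places t5 at 6 to 8 days post-stroke. Four days earlier is about days 2 to 4 if no weekend intervenes, so session 1 falls in or near that window and session 5 after it.

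At stake is a mechanistic statement. A difference caused by recovery, adaptation or the measurement set-up could be reported as an effect of exercising for longer, or could hide such an effect.

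**Working it through.** **1. The plan's own durations.** 2 bouts × 5 min = 10 min in session 1, and 6 × 5 = 30 min in session 5. Both figures reproduce.

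**2. What changes between the two sessions.**

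| Factor | Session 1 | Session 5 | Difference |
|---|---|---|---|
| Prescribed exercise (Section 12.3.3) | 10 min | 30 min | 20 min |
| Sessions already completed (Section 12.3.3) | 0 | 4 | 4 |
| Days since stroke (Sections 12.3.3, 14.2.1) | d | d + 4 or more | at least 4 |
| Face mask and gas analysis (Table 4) | no | yes | 1 |

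**3. Identification.** Let R be the change in CBF velocity from same-day rest. If the factors act additively, each participant gives one paired difference:

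R5 − R1 = 20·β(duration) + g·β(day) + 4·β(prior sessions) + 1·β(mask) + error, with g ≥ 4.

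That is one equation with four unknowns.

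- Design matrix for sessions 1 and 5 (intercept, duration, day, prior sessions, mask): rank 2 of 5.
- Pooled over 12 participants with participant effects, staggered start days (assumed) and g = 4 for all: rank 13 of 16, that is, 12 participant effects plus one contrast.
- If a weekend makes g differ between participants, the day term could be separated. Duration, prior sessions and mask still differ by 20, 4 and 1 in everyone as prescribed, so they remain inseparable.
- Measuring CBF velocity in all five sessions would not be enough. Duration (10, 15, 20, 25, 30) and prior sessions (0, 1, 2, 3, 4) rise in lockstep: rank 2 of 3 with the intercept.

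**4. What this could do to a test (assumed range).** The protocol gives no size for the non-duration effects. Suppose duration has no effect and the other three together shift R5 − R1 by b SDs of the paired difference. The rejection probability of a two-sided 5% paired t-test comes from the noncentral t with n − 1 degrees of freedom and noncentrality b√n. Section 7.3 gives 12 per arm as the minimum. The target of 30 (24 ÷ 0.8) gives 15 per arm.

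| b (assumed) | n = 12 | n = 15 |
|---|---|---|
| 0.25 | 12% | 15% |
| 0.5 | 35% | 44% |
| 1.0 | 88% | 95% |

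The 95% confidence interval half-width, t(0.975, n − 1)/√n, is 0.64 SD at n = 12 and 0.55 SD at n = 15. More participants narrow the interval around the combined effect but do not separate its parts.

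**5. What the recorded data can do.** CBF velocity is recorded throughout both sessions. Take values at minutes 5 and 10 of session 1 and minutes 5, 10, 20 and 30 of session 5, and fit an intercept, a session indicator and minutes of exercise. The design has full rank, 3 of 3. A slope over exercise time is then estimable, provided the day, training and mask bundle acts as a constant shift between sessions.

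**The case against.** The strongest reply has four parts.

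- **The remark is modest.** It is a hedged aside in a justification table. Objective 3a is to measure the acute physiological response, and dose-response appears in no aim or objective. This stands. A reader might infer that the Aim 3 mechanistic analysis fails. It does not: the rest-to-exercise response and the resting comparison between arms are untouched.
- **The outcome is a change from same-day rest, and controls supply resting values at both times.** This also stands for additive drift in the resting level. A reader might argue that a few percent of drift could produce or cancel the 9% increase cited in Section 4.5 (n = 4). The documents do not support that. Resting drift of this kind is subtracted out, the 9% is a rest-to-exercise rise rather than a 10-versus-30-minute difference, and no drift in the response to exercise is quantified.
- **CO₂ is partly on the causal pathway.** The protocol describes exercise raising CO₂ production and CO₂ regulating CBF. A reader might call the lack of end-tidal CO₂ in session 1 an uncontrolled confounder, but adjusting for it could remove part of the effect of interest. Its absence limits interpretation and no more. Nor does the protocol say that a mask alters CBF velocity; that is only possible.
- **No estimator is fixed, and the analysis plan is not at hand.** A bout-matched analysis remains open. But the protocol does name both the contrast and the meaning it will be given, and a later model for that contrast cannot supply the missing separation.

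It is also fair that the tie between duration and session describes the prescription. Delivered duration may vary through early stopping, but not at random, so this does not cure the confounding.

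**Conclusion.** The point holds. The session 1 versus session 5 contrast estimates the combined effect of duration, day since stroke, prior training and mask, and cannot be read as a duration effect. Even without confounding, two prescribed durations could show a difference but not the shape of a dose-response.

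Severity is minor to moderate. The statement is exploratory, supports only part of objective 3a and affects none of the progression criteria in Section 6.3. The non-identification follows from the prescribed schedule alone. The rejection rates in the working rest on assumed shifts of 0.25 to 1.0 SD and show how misattribution could arise, not how large it will be.

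A reader might also infer that the trial's data cannot address duration at all. They can in part, because recording is continuous; the fault lies in the stated contrast and its interpretation.

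**What to change.** In Table 4, stop attributing the session 1 versus session 5 contrast to duration. Describe it as a combined duration, day, training and mask difference. Then, from the CBF velocity already recorded:

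1. Compare the change from same-day rest at matched times, bouts 1–2 of session 1 against bouts 1–2 of session 5, and label the result as the combined day, training and mask difference.
2. Estimate the time course within session 5, for example at 10, 20 and 30 cumulative minutes (ends of bouts 2, 4 and 6), in a repeated-measures model, as the exploratory duration response. Day, number of prior sessions and mask are constant there.

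**Cost.** No new measurements; a sentence or two in Table 4 or the analysis plan.

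**Limits to state with it.** The second analysis measures response to time in exercise within a session, which is not the same quantity as the response to a longer session. It also tracks fatigue and the gear changes made to hold perceived exertion. Pooling both sessions separates duration only if the day, training and mask bundle acts as a constant shift. Participants who do not reach session 5, for example after early discharge, do not contribute to the session 5 analyses; the planned contrast has the same loss.

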9.3. Scheduling research activity

Research team members will liaise with clinical staff to decide upon the most suitable times to conduct research activity. Key factors to consider will include patient clinical status, patient wellbeing and fatigue, and scheduled routine care.

9.4. Participant food and drink consumption

Participants will not be asked to alter their food intake. Participants will be politely asked to refrain from consuming caffeinated beverages prior to any research activity on the second and sixth study days, where CBF will be measured. Caffeine is a cardiovascular stimulant (114). In patients recovering from an acute ischaemic stroke, ingestion of 250 mg caffeine (approximately 2.5 cups of coffee) reduces CBF velocity and global blood flow by 13-30% (115). Restriction of caffeine intake will therefore improve the validity of CBF measurements. The research team will liaise with clinical and catering staff to ensure that this request is communicated. Alternative decaffeinated beverages will be offered instead. However, if participants refuse to restrict caffeine intake, they will not be excluded from the study. Data obtained from these participants will be interpreted with caution and this will be noted as a limitation of the study.

9.5. Preparation, storage and analysis of blood samples

Venous blood samples will be taken at t_5 (6-8 days post-stroke). Baseline blood samples will be collected from control and intervention group participants in a resting state. Post-exercise blood samples will be taken from the intervention group participants during the recovery (passive cycling) phase following aerobic exercise.

Blood samples will then be centrifuged and aliquoted at RHH. Processed samples will then either be stored in a designated -80°C freezer at RHH or put on ice (for up to 5 hours) and transferred to the AWRC and stored at stored at -80°C. mBDNF will be measured using an enzyme-linked immunosorbent assay (116). Platelet count will be measured using an automated haematology analyser. Blood plasma volume will be measured using the Dill and Costill method (117). Blood samples will be stored for 10 years to allow time to source additional funding and obtain ethical approval for further exploratory analyses that may improve mechanistic knowledge. 10 years after the trial end date samples will be destroyed in accordance with local laboratory procedures. Researchers are trained in venepuncture.

10. COVID-19 contingency plan

Currently, non-essential face-to-face research is suspended due to the COVID-19 pandemic. A restart date has not yet been announced, however it is unlikely that the proposed study will be able to take place before the end of 2020 due to the combination of winter pressures and a second wave of COVID-19-related hospital cases. If the proposed study is approved and is able to commence in the early months of 2021, we anticipate that patient follow-up appointments will be conducted virtually (via video call or telephone) for a transitional period of an unknown duration. Thus, the research activities that are planned to be conducted at follow-up appointments may be adapted or omitted. Table 5 outlines our contingency planning for research-related activities. In line with STH procedures, participants will be given an information leaflet providing technical support with regards to video call and telephone consultations. All face-to-face research activities will be conducted in accordance with STH risk management policy.

Table 5. COVID-19 contingency plan

Activity/measure	Plan A (no face-to-face research restrictions)	Plan B (COVID-19 restrictions)
National Institutes of Health Stroke Scale (NIHSS)	Face-to-face assessment conducted at the 3-month follow-up appointment by [name].	Only possible to conduct via high-quality video call . This will be dependent on if the participant has access to a device with high-quality video calling function. This assessment will be conducted by [name]. If the video quality is deemed to be poor, this assessment will be omitted.
Barthel Index	Conducted at the 2-week and 3-month follow-up appointments via face-to-face interview by [name].	Conducted at the 2-week and 3-month follow-up appointments via telephone or video call interview by [name].
Thigh muscle ultrasound	Conducted at the 3-month follow-up appointment. Requires physical contact.	Omitted.
Physical function assessments (SPPB,	Conducted at the 3-month follow-up appointment. Requires direct	Omitted.

10-m walk, handgrip strength)	supervision and in some cases, physical assistance.	
Acute fatigue (RoFS)	Simple visual analogue scale conducted before and after physical function assessments at the 3-month follow-up appointment.	Omitted.
Modified Rankin Scale	Conducted at the 2-week and 3-month follow-up appointments via face-to-face interview by [name].	Conducted at the 2-week and 3-month follow-up appointments via telephone or video call interview by [name].
Cognitive function (MoCA)	Conducted at the 3-month follow-up appointment. Requires direct supervision.	Omitted.
Chronic fatigue (FSS) Anxiety and depression (GAD-7, PHQ-9)	Conducted at the 3-month follow-up appointment via face-to-face interview by [name].	Conducted at the 3-month follow-up appointment via telephone or video call interview by [name].
Optimism (rLOT) Health-related quality of life (EQ-5D) Exercise self-efficacy Post-discharge physical activity (GPAQ)	Conducted at the 3-month follow-up appointment via face-to-face interview by [name].	Conducted at the 3-month follow-up appointment via telephone or video call interview by [name].
Wrist-based accelerometer	Participant to bring activity monitor to 2-week appointment and hand over to [name].	Participant will be provided with a pre-paid envelope to post the activity monitor back to the research team.
Qualitative interview	Face-to-face interview to be conducted by [name] at the 3-month follow-up appointment.	Conducted at the 3-month follow-up appointment via telephone or video call interview by [name].

11. Feasibility outcome measures

Table 6. Feasibility outcome measures

Outcome	Description
Recruitment rate	Number of participants recruited per month of the recruitment period.
Exclusion rate	Number of ineligible patients divided by the total number of patients admitted to the RHH stroke service during the recruitment period.
Consent rate	Percentage of eligible patients who consent to participate.
Dropout rate	Percentage of individuals that discontinue participation after the study has commenced. Voluntary reasons for dropout will be recorded. Early discharge from hospital will not count as a dropout.
Participant fidelity	Completion of key exercise components in accordance with the exercise protocol including: percentage of planned exercise session duration completed, percentage of target exercise intensity per session attained, and percentage of total planned exercise sessions completed.
Completeness of data	Percentage of planned measurements completed and recorded.
Safety	Number of SAE and AEs related to the intervention.
Acceptability of intervention (participant interview)	Comfort and ease of using cycling apparatus.
Acceptability of study procedures (healthcare professional interview)	
 • Attitudes towards the intervention • Burden on staff and participants • Perceived effectiveness of the intervention

12. Intervention

